7. DEFINITIONS AND DERIVED VARIABLES

7.1. Age

Age will be calculated using the Date of Birth (DOB) and the date of the consenting the subject and presented as age at last birthday as an integer.

Age = Integer part of [(Date of Baseline visit – Date of Birth) / 365.25]

7.2. Iris Color

Iris color will categorized into either dark or light based on the subjects hue and lightness of their iris using Johnson & Jonsons Iris Color Scale. If hue is brown or lightness is dark then the subject will be classified as having a dark iris, if hue is light then the subject will be classified as having a light iris. If lightness is medium and hue is green, blue or grey then the suject will be classified as having a light iris; otherwise subjects will be classified as having a dark iris.

7.3. Visit Windows

Table 4: Visit Window information

Scheduled Visit Number	Time Interval (label on output)	Time Interval (Day) ^a	Target Time Point
1	Baseline	1	1
1	Fitting	1	1
2	2-Week FU	13 to 15	14
2	Fitting	13 to 15	14
3	2-Week FU	13 to 15	21
3	Fitting	13 to 15	21
4	2-Week FU	13 to 15	28

^a The first treatment day is Day 1.

8. GENERAL STATISTICAL CONSIDERATIONS

8.1. Statistical Software

All data summaries and statistical analyses will be performed using the SAS software Version 9.4 or higher (SAS Institute, Cary, NC)².

8.2. Summary Statistics

Throughout the analysis of data, the results for each subject/eye will be used when available for summarization and statistical analysis. Unscheduled visits will be summarized separately and will be excluded from the statistical analysis.

Summary tables (descriptive statistics and/or frequency tables) will be provided for all baseline variables, efficacy variables and safety variables, as appropriate, by study lens at each time event (fitting and follow-up). Continuous variables will be summarized with descriptive statistics (n,

mean, standard deviation [SD], median, minimum and maximum). Frequency count and percentage of subjects or eyes within each category will be provided for categorical data.

8.3. Reporting Numerical Values

Means, medians and confidence/credible intervals will be reported to one decimal place greater than the original data. The standard deviation will be reported to two decimal places greater than the original data. Minimum and maximum will use the same number of decimal places as the original data. P-values greater or equal than 0.0001 will be reported to 4 decimal places; p-values less than 0.0001 will be reported as “<0.0001”. All percentages will be reported to one decimal place.

8.4. Sample Size Justification

This study was designed and powered to show non-inferiority of the Test lens compared to the Control lens with respect to logMAR Visual Acuity, Slit Lamp Findings (Grade 3 or higher), CLUE comfort, handling and overall quality of vision. It was assumed there was no difference between the Test and Control lens with respect to visual acuity and slit lamp findings. Based on data from 3 historical studies, it was assumed there was a 5-, 3- and 4-point difference between the Test and Control lenses with respect to CLUE comfort, handling and overall quality of vision, respectively.

In addition to the endpoints mentioned above this study was also powered to demonstrate non-inferiority of the Test lens relative to the Control lens with respect to vision satisfaction in bright lighting, overall quality of vision indoors and the proportion of eyes with acceptable fitting while the Test lens is significantly superior to 90%. Unless otherwise specified, the sample size was calculated to achieve a minimum statistical power of 80% and a type I error of 5%.

A total of 5 historical studies were utilized in the sample size calculation. Table 5 displays the studies, their corresponding study design and the number of subjects enrolled and completed per-protocol.

Table 5: Historical Studies Included in Sample Size Calculation

Study	Study Design	Endpoints Collected	No. Enrolled	No. Completed Per-Protocol
████████	2X3 Crossover	CLUE, SLF, Lens Fit	135	132
████████	2X3 Crossover	CLUE, Visual Acuity (logMAR), SLF, Lens Fit	133	121
████████	2X3 Crossover	CLUE, SLF, Lens Fit	92	78
████████	Single-Arm	SLF, Lens Fit	54	48
████████	Single-Arm	SLF, Lens Fit	56	41

Table 6: Descriptive Summary of CLUE Scores by Domain Pooled Across Historical Studies

████████ – 2-Week Follow-up Evaluation

CLUE Domain [Mean(SD) ¹]	Test	Control
Comfort	66.46 (22.20)	61.19 (24.20)
Handling	69.61 (19.18)	66.79 (20.01)
Overall Quality of Vision	64.15 (18.83)	60.33 (22.29)

¹SD = Standard Deviation

Table 7: Descriptive Summary of Visual Acuity (logMAR) - █ – 2-Week Follow-up Evaluation

Visual Acuity High Illumination High Contrast [Mean(SD) ¹]	Test	Control
	-0.0928 (0.08253)	-0.0726 (0.08011)

¹SD = Standard Deviation

Table 8: Descriptive Summary of Mechanical Lens Fitting Pooled Across all Historical Studies

Any Unacceptable Lens Fit ¹ [n(%)]	Test n (%)	Control n (%)
Fitting Evaluation	0 (0.0)	0 (0.0)
2-Week Follow-up	1 (0.05)	0 (0.0)

¹The percent of any unacceptable fit is calculated using Total Unique eyes as a denominator

Table 9: Descriptive Summary of Slit Lamp Findings Pooled Across all Historical Studies

SLF Grade 2	Test n (%)	Control n (%)
Corneal Edema	0 (0.0)	0 (0.0)
Conjunctival Injection	55 (8.09)	59 (21.85)
Tarsal Abnormalities	51 (5.93)	24 (8.89)
Corneal Neovascularization	0 (0.0)	0 (0.0)
Corneal Staining	2 (0.29)	0 (0.0)
Other Findings	0 (0.0)	0 (0.0)
Total Eyes (N)	680	270
Any SLF Grade 2 ²	108 (15.8)	83 (33.74)
Any SLF Grade 3+	0 (0.0)	0 (0.0)
Total Unique Eyes	680	270

Total Unique Subjects	340	135
-----------------------	-----	-----

%= nx100/N; SD=Standard Deviation

¹All SLF reported for this study are combined for the purposes of summarizing

² The percent (%) of Any Grade 2 is calculated using the Total Unique Eyes as the denominator

Table 10: Descriptive Summary of Individual Items from [REDACTED] – 2-Week Follow-up

Questionnaire Item/ Response	Test	Control
Vision Satisfaction in Bright Light [n(%)]		
Strongly Agree	65 (35.9)	35 (19.2)
Agree	89 (49.2)	95 (52.2)
Neither Agree Nor Disagree	24 (9.92)	17 (9.3)
Disagree	13 (7.2)	29 (15.9)
Strongly Disagree	0 (0.0)	6 (3.3)
Overall Quality of Vision Indoors [n (%)]		
Excellent	100 (55.2)	80 (44.0)
Very Good	55 (30.4)	62 (34.1)
Good	23 (12.7)	30 (16.5)
Fair	3 (1.7)	7 (3.9)
Poor	0 (0.0)	3 (1.65)

CLUE Comfort

Sample size calculation for CLUE comfort was carried out using an approximation of the power of an F-test derived from the non-centrality parameter calculated from the observed F statistic of a linear model³.

Model details:

CLUE comfort was analyzed using a linear mixed model. Lens type was included as the only fixed effect. An unstructured (UN) covariance matrix was used to model the correlation between measurements on the same subject across study periods. Below is the variance-covariance matrix used in the CLUE Comfort model.

$$\sum_{comfort} \begin{pmatrix} 397.18 & 142.48 & 144.55 \\ 142.48 & 411.89 & 210.90 \\ 144.55 & 210.90 & 370.83 \end{pmatrix}$$

Visual Performance (logMAR)

Sample size calculation for visual performance (logMAR) was carried out using an approximation of the power of an F-test derived from the non-centrality parameter calculated from the observed F statistic of a linear model³.

Model details:

visual performance was analyzed using a linear mixed model. Lens type was included as the only fixed effect. A compound symmetric (CS) covariance matrix was used to model the correlation between measurements on the same subject across study periods. Below is the variance-covariance matrix used in the visual performance model.

$$\sum_{\text{visual performance}} \begin{pmatrix} 0.003518 & 0.000374 & 0.000374 \\ 0.000374 & 0.003518 & 0.000374 \\ 0.000374 & 0.000374 & 0.003518 \end{pmatrix}$$

Acceptable Lens Fit

Acceptable lens fit is a binary response as $y=1$ if a subject eye has an acceptable fit and $y=0$ otherwise. Indicated by the historical data there was only 1 observed unacceptable lens fittings for the Test lens therefore, the common reference rate of 95% was selected for the sample size calculation, since this is considered to be a more conservative reference proportion. Assuming a correlation 0.80 between measurements within the same subject and period (intra-eye correlation); and assuming a correlation of 0.50 between measurements within the same subject across periods. A total of 2000 replicating trials were simulated to estimate a sample size with a minimum statistical power of 80%.

Slit Lamp Findings

There were no Grade 3 or higher SLFs observed in any of the historical studies. Assuming no difference between study lenses and a correlation 0.80 between left and right eyes within the same subject and period; and a correlation of 0.50 between measurements within the same subject across periods (intra-subject correlation). A reference rate of no more than 5% was assumed (worse-case scenario) with a non-inferiority odds ratio margin of 2. A total of 2000 replicating trials were simulated, each replicated sample was analyzed using a generalized estimating equation (GEE) model with a binary distribution and the logit as the link function. Each model included lens type as the only fixed, eye was included as a random effect. The Odds ratio and corresponding 95% confidence interval was used estimate differences between the Test and Control lenses. The upper limit of each 95% confidence interval was compared to 2; if the upper limit was below 2 then NI=1; otherwise NI=0. Statistical power was calculated at the average NI. A sample size of 50 was chosen to achieve a minimum statistical power of 80%.

The non-inferiority odds ratio margin of 2 corresponds to no more than a 5% difference between the Test and Control lenses assuming the Control reference rate does not exceed 5%.

Individual Questionnaire Items

Overall quality of vision outdoors and vision satisfaction in bright lighting sample size estimates were calculated using historical data from [REDACTED]. One-thousand boot strap samples were simulated based on the historical data. For each replicated sample a generalized linear mixed model was used with a multinomial distribution and the cumulative logit as the link function. Lens wear sequence, lens type, period and first order carryover effect were included in the model as fixed effects. A variance component (VC) covariance structure was used to model the measurements between subjects across study periods.

The non-inferiority cumulative odds ratio margin of 0.67 corresponds to no more than a 10% difference between the Test and Control lenses assuming there is no difference between study lenses.

Table 11: Sample Size Estimates and Power Calculations for Primary Endpoints

Endpoint	Number per Subjects to Complete	Power
Distance Monocular Visual Acuity (logMAR)	4	80%
SLFs (Grade 3 or Higher)	50	80%
Acceptable lens Fit	65	80%
CLUE Comfort	30	87%
Vision Satisfaction in Bright Lighting	48	81%

Table 12: Sample Size Estimates and Power Calculations for Secondary Endpoints

Endpoint	Number per Subjects to Complete	Power
CLUE Handling	30	81%
CLUE Overall Quality of Vision	30	82%
Overall Quality of Vision Indoors	95	81%

As indicated in Table 11 and 12 above, the sample size chosen for this study was primarily driven by overall quality of vision indoors. The plan is to enroll 120 eligible subjects with a target of 105 subjects to complete the study. During the enrollment period, the subject drop-out rate will be closely monitored, if an unexpectedly high dropout rate is observed, then the targeted total enrollment number may be increased accordingly to ensure that a minimum of 105 subjects complete the study.

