5. STATISTICAL HYPOTHESES FOR STUDY OBJECTIVES

5.1. Primary Hypotheses

All primary hypotheses must be met in order to satisfy the primary objective of this study.

1. The Test lens will be non-inferior to the Control lens with respect to Distance Monocular logMAR Visual Acuity at the two-week follow-up evaluation under both lighting conditions (Bright illumination low contrast and dim illumination high contrast). A non-inferiority margin of 0.05 logMAR will be used.

2. The Test lens will be non-inferior to the Control lens with respect to the percentage of eyes with Grade 3 or higher Slit Lamp Findings (Biomicroscopy) across all follow-up visits (scheduled and unscheduled). A non-inferiority odds ratio margin of 2 will be used.
3. The proportion of eyes with acceptable fit will be greater than 90% across all visits (scheduled and unscheduled) for all subjects wearing the Test lens.
4. The Test lens will be non-inferior to the Control lens with respect to CLUE Overall Comfort at the two-week follow-up evaluation. A non-inferiority margin of -5 points will be used.
5. The Test lens will be non-inferior to the Control lens with respect to Vision satisfaction in bright lighting at the two-week follow-up evaluation. A non-inferiority cumulative odds ratio margin of 0.67 will be used.

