8.5. Statistical Significance Level

All planned analysis will be conducted with an overall type I error rate of 5%. There will be neither adjustment for multiple tests nor adjustment for multiplicity of endpoints. Unless otherwise specified, all statistical tests will be 2-sided.

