We assume random subject eye effects are independent and identically distributed (i.i.d) as $\alpha_j \sim N(0, \sigma_{eye}^2)$ and the random subject effect is i.i.d. as $\delta_m \sim N(0, \sigma_{subject}^2)$ and the random site effect is i.i.d as $\gamma_l \sim N(0, \sigma_{site}^2)$ for $i=1,2$ (lens), $j=1, 2$ (eye), $k=1, 2$ (sequence), carry1=1, 2 (first-order carryover effect) and $l=1\dots|m_l(\text{subject/site})$ and $l=1, 2, 3, 4, 5$ and 6 (site).

For the β coefficients, independent non-informative priors $N(0, 1000)$ will be used. For the variance of random effects σ_{eye}^2 and σ_{site}^2 independent non-informative conjugate priors inverse-gamma(0.001, 0.001) will be used. For Σ , non-informative conjugate priors inverse-wishart(3,S) will be used where S is a 3X3 variance-covariance matrix of y_{ijklm} . The metropolis sampler algorithm as implemented in the SAS/STAT MCMC 14.2¹⁴ procedure will be used to estimate the posterior distribution of the unknown parameters. Inferences will be made based on the 95% posterior credible intervals for relevant parameters.

Hypothesis Testing

The null and alternative hypothesis for visual acuity (logMAR) to test for non-inferiority of the Test lens relative to the Control lens is as follows:

$$\begin{aligned} H_0: \beta_1 &\geq 0.05 \\ H_A: \beta_1 &< 0.05 \end{aligned}$$

Non-inferiority will be declared if the upper limit of the 95% credible interval of the difference between the Test and Control is below 0.05, i.e. $P(\beta_1 < 0.05) \geq 0.975$.

CLUE Overall Comfort

CLUE Comfort scores will be analyzed using a Bayesian multivariate normal random-effects model to compare the Test and Control lenses. The regression model will include baseline CLUE comfort scores, sequence of lens wear, lens type and first-order carryover effect as fixed effects. Clinical site will be included as random effects. Other subject characteristics such as age, gender, race and iris category will be included when appropriate.

The Model:

Let $y_{ijkl} = (y1_{ijkl}, y2_{ijkl}, y3_{ijkl})$ denote the CLUE Comfort score for the l^{th} subject at the k^{th} site, assigned to the i^{th} lens using the j^{th} sequence at periods 1, 2 and 3. The likelihood for y_{ijkl} is constructed as follows:

$$y_{ijkl} \sim N(\mu_{ijkl}, \Sigma)$$

Where $\mu_{ijkl} = (\mu1_{ijkl}, \mu2_{ijkl}, \mu3_{ijkl})^T$ and Σ is a 3X3 variance-covariance matrix. Here,

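### The stated 4 subjects for 80% power on logMAR acuity does not follow from the printed covariance matrix and the no-difference assumption; the row needs restating, the enrolment target does not

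*SAP*

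**What the plan says.** SAP section 8.4 (repeated in protocol section 14.2) gives these planning inputs for acuity:

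- True difference: "It was assumed there was no difference between the Test and Control lens with respect to visual acuity and slit lamp findings".
- Error rates: "the sample size was calculated to achieve a minimum statistical power of 80% and a type I error of 5" per cent. Sidedness is not stated there, but section 8.5 adds: "Unless otherwise specified, all statistical tests will be 2-sided".
- Model: a linear mixed model whose sole fixed term is lens type. On the covariance the SAP says: "A compound symmetric (CS) covariance matrix was used to model the correlation between measurements on the same subject across study periods". The matrix has 0.003518 on the diagonal and 0.000374 off it.
- Margin (section 5.1): "A non-inferiority margin of 0.05 logMAR will be used". It applies under both lighting conditions.
- Decision rule (section 11.1): "Non-inferiority will be declared if the upper limit of the 95% credible interval of the difference between the Test and Control is below 0.05", which corresponds to one-sided 2.5%.

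Table 11 then lists 4 subjects and 80% power for acuity. The only historical acuity data shown (SAP Table 7) are headed "Visual Acuity High Illumination High Contrast", with Test -0.0928 (SD 0.08253) and Control -0.0726 (SD 0.08011). The trial itself tests bright illumination with low contrast, and dim illumination with high contrast.

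**The concern.** Acuity is a primary endpoint, and every primary hypothesis has to be met. A reader should be able to get from the stated difference, margin, covariance and alpha to the stated sample size, and here that cannot be done. The standard error of the lens effect with 4 subjects is about two thirds of the margin, so 80% power under no difference is not plausible at first sight. The justification also rests on data from a condition that is neither of the two being tested. What is at stake is whether the stated power can be trusted and traced, not whether enough subjects are being recruited.

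**Working it through.** **Inputs.** Variance v = 0.003518 and covariance c = 0.000374 (SAP 8.4), so SD = 0.0593 and correlation = 0.000374/0.003518 = 0.106. Margin 0.05 (SAP 5.1). True difference 0 (SAP 8.4). Sequences Test/Control/Control and Control/Test/Test, allocated equally (SAP 3.4).

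**Standard error** by generalised least squares, lens as the only fixed effect, one measurement per subject and period.

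- Within-subject variance: v - c = 0.003144. Each sequence contributes a lens sum of squares of 2/3, so information per subject is (2/3)/0.003144 = 212.04.
- Between-subject part: variance of a subject mean is 0.000374 + 0.003144/3 = 0.001422. The proportion of periods on Test is 1/3 or 2/3, a deviation of 1/6, so information per subject is (1/36)/0.001422 = 19.53.
- Total 231.58 per subject. SE at n = 4: 1/√(4 × 231.58) = 0.0329. Losing the between-subject part, as with a sequence term, gives 0.0343.

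**Check of the method on a row that can be reproduced.** The same calculation on the printed comfort matrix with 30 subjects in total gives SE 3.653. The distance from the margin is 5 + 5 = 10, or 5 + 5.27 = 10.27 using the unrounded historical means (66.46 - 61.19). By non-central t, power is 85-87% at one-sided 5% and 75-79% at one-sided 2.5%, against 87% stated. So the method is of the right kind, the table counts total subjects, and the comfort row appears to use one-sided 5%.

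**The acuity row.** Power = P(T > critical value) with non-centrality (0.05 + Test advantage)/SE. The low end of each range uses a t distribution with (units - 2) df; the high end is the normal approximation. For example, 0.05/0.0329 = 1.52; 1.52 - 1.96 = -0.44, giving 33%; 1.52 - 1.645 = -0.12, giving 45%.

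| 4 subjects in total | SE | One-sided 2.5% | One-sided 5% |
|---|---|---|---|
| No difference, one measurement per period | 0.0329 | 15-33% | 27-45% |
| No difference, 8 independent eyes | 0.0232 | 44-58% | 60-69% |
| 0.0202 Test advantage, one measurement per period | 0.0329 | 24-57% | 42-69% |
| 0.0202 Test advantage, 8 independent eyes | 0.0232 | 71-86% | 84-92% |

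No no-difference variant reaches 80%. The closest match to the stated figure is independent eyes with the observed advantage (-0.0726 + 0.0928 = 0.0202) at one-sided 2.5%: 80.6% with 15 df. Correlated eyes with the same advantage also come near: 77-82% at between-eye correlation 0.106 and one-sided 2.5%, and 76-80% at correlation 0.5 and one-sided 5%. These correlations are assumptions.

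**Subjects needed for 80% with no difference.** By the normal approximation, n = (z for alpha + 0.842)²/(0.05² × 231.58), where 0.05² × 231.58 = 0.579.

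- One-sided 2.5%: 7.849/0.579 = 13.6, so 14; with t corrections, up to 16.
- One-sided 5%: 6.183/0.579 = 10.7, so 11; with t corrections, up to 13.
- Both eyes counted as independent: 7-8 and 6-7. With between-eye correlation 0.80, the value the SAP gives for slit lamp findings and assumed here for acuity: 13 and 10.

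**At 105 completers,** no difference, one-sided 2.5%. On the printed matrix SE = 1/√(105 × 231.58) = 0.0064. Scaling to SD 0.083 at the same correlation gives SE 0.0090; 0.05/0.0090 = 5.6, so power is above 99.9%. For larger SDs, which are assumptions, power per condition is 97% at 0.12, 82% at 0.16 and 64% at 0.20.

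**The case against.** Several points on the other side have weight.

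- *The alpha is unclear.* The comfort row fits one-sided 5%, not the 2.5% implied by the decision rule. This stands, and it is why both are shown. A reader might want to write in 16 subjects as the right answer, but that is only the upper end for one alpha and one unit.
- *Acuity is measured per eye.* True, and no between-eye correlation for acuity is given. Counting both eyes lowers the number needed, but even fully independent eyes leave 4 subjects at 69% or less.
- *The figure may be per sequence.* Eight subjects with independent eyes and no difference give 81-86% at one-sided 2.5%, and the column heading is garbled. But the comfort row reproduces as a total, and section 8.4 treats the 95 for vision indoors as driving the total of 105.
- *It may be a wording conflict.* The method description refers to an observed F statistic, so the historical difference may have gone in. That is plausible but is not stated, and the closest match needs a different alpha from the comfort row. Either way the text and the figure disagree.
- *The variance.* A reader might infer that the matrix is wrong because its SD (0.059) is below the Table 7 SDs (0.080-0.083). The documents do not support this: they do not say which data the matrix was fitted to or which variance components had been separated out.
- *The untested condition is labelled openly,* and only one historical study is listed as collecting logMAR acuity. This stands as a limitation to declare, not an inconsistency.

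**Conclusion.** The row of 4 subjects and 80% power is not a property of the stated inputs. Under the no-difference assumption the power with 4 subjects is 15-33% (one-sided 2.5%) or 27-45% (one-sided 5%) with one measurement per subject and period, and at most 58% or 69% if all 8 eyes are treated as independent. This rests on the printed matrix, lens type as the only fixed effect, equal sequences and the table counting total subjects.

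The acuity planning data shown are from neither tested condition; how far variability differs under low contrast or dim light cannot be judged from the documents.

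A reader might infer that the trial is underpowered for acuity. The documents do not support that: at 105 completers power is above 99% at the Table 7 SDs, taking the matrix correlation of 0.106, and falls to about 80% only if the SD is roughly double those values. The point is minor and concerns the stated figures.

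**What to change.** In SAP Table 11 and protocol Table 10, do one of two things:

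1. Restate the acuity row under no difference, naming the alpha and the unit (subject or eye). With one measurement per subject and period that is about 14-16 subjects at one-sided 2.5%, or about 11-13 at one-sided 5%. If both eyes are counted, state the between-eye correlation and give the smaller number that follows.
2. If a Test benefit was in fact used, correct the no-difference sentence to give its size, and state the alpha and the treatment of eyes.

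In either case, add the power at 105 completers using the Table 7 SDs, note that these data are for high illumination and high contrast, and justify or give a range for the variability expected under the two tested conditions. Say which data and variance components the matrix reflects, so that its SD of 0.059 can be read against Table 7.

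The cost is a few lines of text. Enrolment, margin and analysis stay as they are.

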2.3. Hypotheses

Primary Hypotheses

All primary and secondary hypotheses must be met to satisfy the objective the study.

Primary Hypotheses	
Endpoint	Hypothesis
Monocular logMAR visual acuity	The Test lens will be non-inferior to the Control lens with respect to Distance Monocular logMAR Visual Acuity at the two-week follow-up evaluation under both lighting conditions (Bright illumination low contrast and dim illumination high contrast). A non-inferiority margin of 0.05 logMAR will be used.
Biomicroscopy	The Test lens will be non-inferior to the Control lens with respect to the percentage of eyes with Grade 3 or higher Slit Lamp Findings (Biomicroscopy) across all follow-up visits (scheduled and unscheduled). A non-inferiority odds ratio margin of 2 will be used.
Fit acceptance rate	The proportion of eyes with acceptable fit will be greater than 90% across all visits (scheduled and unscheduled) for all subjects wearing the Test lens.
Overall CLUE comfort	The Test lens will be non-inferior to the Control lens with respect to CLUE Overall Comfort at the two-week follow-up evaluation. A non-inferiority margin of -5 points will be used
Vision Satisfaction in Bright Lighting	The Test lens will be non-inferior to the Control lens with respect to Vision satisfaction in bright lighting at the two-week follow-up evaluation. A non-inferiority cumulative odds ratio margin of 0.67 will be used.

Secondary Hypotheses

Secondary Hypotheses	
Endpoint	Hypothesis
Overall CLUE Vision	The Test lens will be non-inferior to the Control lens with respect to CLUE Overall quality of vision at the two-week follow-up evaluation. A non-inferiority margin of -5 points will be used.
Overall CLUE handling	The Test lens will be non-inferior to the Control with respect to CLUE Handling at the two-week follow-up evaluation. A non-inferiority margin of -5 points will be used.
Overall Quality of Vision Indoors	The Test lens will be non-inferior the Control lens with respect to Overall quality of vision indoors at the 2-week follow-up evaluation. A non-inferiority cumulative odds ratio margin of 0.67 will be used.

Other Hypotheses

Other Observations	
Endpoint	Hypothesis

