3. STUDY DESIGN

3.1. Overview

This study is a randomized, 4-visit, partially subject-masked, 2x3 bilateral crossover, dispensing trial. Approximately 120 subjects will be screened and enrolled to ensure that at least 105 subjects complete.

The study begins with an initial visit (Visit 1). If a subject is found to meet all eligibility criteria, they will be randomized to one of two lens wear sequences (Test/Control/Control or Control/Test/Test).

If the subject is dispensed their first study lenses at the initial visit then 3 additional visits will be conducted. Their first follow-up visit will occur at approximately 2-weeks after initial dispensing (Visit 2). At visit 2, subjects will be dispensed their next lens as specified per the randomization. Subjects' follow-up for their second lens will occur approximately 2-weeks after visit 2 (Visit 3). Subjects will be dispensed their last study lens (per the randomization) at visit 3 and will return for their final follow-up visit (visit 4) approximately 2-week after visit 3. Unscheduled follow-up visits may occur during the study. Subjects will be advised to wear the study lenses at least five (5) days per week for at least six (6) hours per day for a period of two-weeks each.

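### The slit lamp and lens fit rows behind the 80% minimum power do not follow from their stated inputs, and no joint power is given for a rule that needs every primary hypothesis

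*SAP*

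**What the plan says.** SAP 8.4 sets the target: "Unless otherwise specified, the sample size was calculated to achieve a minimum statistical power of 80% and a type I error of 5" percent. SAP Tables 11 and 12 then list a number of completers and a power for each endpoint separately.

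- **Primaries:** acuity 4 (80%), slit lamp 50 (80%), fit 65 (80%), comfort 30 (87%), bright-light satisfaction 48 (81%).
- **Secondaries:** handling 30 (81%), overall vision 30 (82%), vision indoors 95 (81%).

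The size is taken from the largest row: "the sample size chosen for this study was primarily driven by overall quality of vision indoors". The plan is then "The plan is to enroll 120 eligible subjects with a target of 105 subjects to complete the study".

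The decision rule is joint. SAP 5.1: "All primary hypotheses must be met in order to satisfy the primary objective of this study". Protocol 2.3 goes further: "All primary and secondary hypotheses must be met to satisfy the objective the study". The SAP states that it supersedes the protocol's statistical section.

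For slit lamp findings both documents assume no lens difference, an odds ratio margin of 2, correlations of 0.80 (eyes within a period) and 0.50 (across periods), and a 95% interval. The SAP assumes a rate of at most 5% and the Protocol at most 10%, yet both print 50 subjects for 80%. For fit the assumed rate is 95% against 90%, with the same two correlations. Protocol 14.5 and SAP 11.1 both switch to Grade 2 or higher if there are too few Grade 3 findings, without saying how few.

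**The concern.** The chance of passing every test cannot exceed that of the weakest test, and is lower unless the tests are completely dependent. A minimum of 80% per endpoint therefore says nothing direct about the chance of meeting the objective, and neither document supplies that figure.

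The surplus of 105 completers over most printed sizes could cover the gap, but only if the printed rows are right. The slit lamp and fit rows are the ones to check, since both are primary and both carry strong within-subject correlation. If they are overstated, a Test lens performing as assumed could miss the primary objective through lack of power, and the miss could be misread as evidence against the new production line.

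**Working it through.** **1. Printed rows at face value.** Scale each row to 105 completers with power = Φ((1.96 + z)·√(105/n₀) − 1.96), where z is the normal quantile of the printed power.

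- Slit lamp: 2.802 × √(105/50) − 1.96 = 2.10, or 98.2%.
- Fit: 2.802 × √(105/65) − 1.96 = 1.60, or 94.5%.
- Bright light: 2.838 × √(105/48) − 1.96 = 2.24, or 98.7%.
- Indoors: 2.838 × √(105/95) − 1.96 = 1.02, or 84.7%.
- The other rows are about 100%.

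All primaries, if independent: 0.982 × 0.945 × 0.987 = 0.92. With the secondaries: 0.917 × 0.847 = 0.78.

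**2. Can the slit lamp row be reproduced?** Let v = p(1 − p), with half the subjects in each sequence. I apply 0.50 to any two records from different periods.

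- Two eyes in one period: variance of the sum v(2 + 2 × 0.80) = 3.6v.
- Four records over two periods: 2 × 3.6v + 2 × 4 × 0.50v = 11.2v.
- Covariance between the two sums: 8 × 0.50v = 4v.
- Test minus Control within a subject: 3.6v + 11.2v − 8v = 6.8v in either sequence.

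Each lens has 3n records, so SE(log OR) = √(6.8/(9nv)) and power = Φ(0.693/SE − 1.96). The last two columns are simulated GEE power with robust limits. The working correlation is not stated in the plan, so both choices are shown.

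| Rate | n | SE | Formula | GEE, independence | GEE, exchangeable |
|---|---|---|---|---|---|
| 5% | 50 | 0.564 | 23% | 28% | 36% |
| 5% | 105 | 0.389 | 43% | 44–46% | 51–55% |
| 10% | 50 | 0.410 | 39% | 41–42% | 53% |
| 10% | 105 | 0.283 | 69% | 67–68% | 79% |

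The printed 80% at 50 is not recovered. Reading 50 as per sequence (100 in total) gives 44–50% at 5% and 66–76% at 10%.

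**3. Can the fit row be reproduced?** Use Test-lens records only, one per eye per Test period. Half the subjects contribute 3.6v and half 11.2v, so the variance of the proportion is 7.4v/(9n), with v = 0.0475.

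- n = 65: SE = 0.0245. Logit scale: Φ(0.747/0.516 − 1.96) = 30%. Proportion scale: Φ(0.05/0.0245 − 1.96) = 53%. Simulated: 30–31% and 56%.
- n = 105: SE = 0.0193. Logit: Φ(0.747/0.406 − 1.96) = 45%. Proportion: Φ(0.05/0.0193 − 1.96) = 74%. Simulated: 47% and 70%.

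A second fit record per eye in each period, also at 0.80, would change little: the variance of a period mean goes from 3.6v/4 = 0.90v to 13.6v/16 = 0.85v. A figure near 80% appeared only on departing from the stated inputs. One such route treats eyes as independent at n = 65 (67–84%).

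**4. Joint power at 105 completers.** The other primaries are near certain: acuity about 100%, comfort 99.9%, bright light 98–100%. They change the products by about a point at most.

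| Case | Slit lamp | Fit | Product |
|---|---|---|---|
| SAP rate, 5% | 45–55% | 47–70% | 21–38% |
| Protocol rate, 10% | 68–79% | 47–70% | 32–54% |
| Grade 2 fallback | 83–100% | 47–70% | 39–70% |

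The fallback range runs from equal Grade 2 rates of 15.8% to the historical rates, 15.8% for Test and 83/270 = 30.7% for Control. Under any dependence the joint power cannot exceed the smaller component, so fit alone holds it to about 47–70% whatever the slit lamp result.

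**The case against.** **The tables are single-endpoint and do not claim joint power.** That is true, and 105 completers exceed every printed size. At face value the SAP's own rule is well covered at 92%; only the Protocol's wider rule falls short, at 78%. It would be wrong to blame the all-must-pass rule for most of the shortfall.

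**The planning values are deliberately cautious.** This stands for fit. The SAP calls 95% conservative and reports one unacceptable Test fit in its historical data. With a logit-scale limit and 105 completers, fit power is about 82–84% at a true 97%, 94% at 98% and 99% at 99%. With 99% fit and the Grade 2 fallback, slit lamp and fit together reach about 82–100%. It does not help the Grade 3 slit lamp test: at an odds ratio of 1, a rate below 5% makes v smaller and the SE larger, so power falls.

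**A reader might infer that the trial has roughly 20% power and cannot exceed about 46%.** The documents do not support that as a general statement. It needs the 5% rate, independence-working GEE, a logit-scale fit limit and no fallback, all together. Historical Grade 3 findings were zero, so the fallback may well be the test that is used.

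**The calculation is not the planned analysis.** SAP 11.1 specifies Bayesian random-effects logistic models. That limits the precision of every figure here. It does not clearly help the plan: a likelihood approximation with a subject random intercept gave slit lamp power of only 13–26% at 105 completers and 5%. SAP 8.4 itself used GEE for its slit lamp sizing.

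**Sidedness.** The decision rules use 95% limits with 0.975 posterior probability, and SAP 8.5 says: "Unless otherwise specified, all statistical tests will be 2-sided". Even with a one-sided 5% limit, fit power at 105 is only 63–77%.

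**Conclusion.** The point holds in this form: the stated 80% minimum is not supported for two primary endpoints, and the joint power of the success rule is missing. The dominant fault is in the slit lamp and fit rows; the intersection of tests adds to it. At the stated inputs and 105 completers, all-primary power is below 80% in every case examined: about 21–38% at the SAP slit lamp rate, 32–54% at the Protocol rate and 39–70% under the Grade 2 fallback.

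These ranges assume independent endpoints for the products, latent-normal or mixture generators for the correlated eyes, one fit record per eye per Test period, and asymptotic limits in place of credible limits. They do not show that the trial is likely to fail: a true fit rate well above 95%, together with the fallback, could bring it above 80%.

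**What to change.** In SAP 8.4:

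1. Recompute and restate the slit lamp and fit rows, giving the model, working correlation and interval scale used.
2. Reconcile the 5% and 10% slit lamp rates between SAP and Protocol.
3. Label Tables 11 and 12 as single-endpoint power.
4. State the probability of meeting all primary hypotheses at 105 completers, from one simulation of the six tests under the SAP 11.1 decision rules, with and without the Grade 2 fallback. Define the count that triggers the fallback. If the Protocol's wider rule is kept, give its joint power too.
5. Remove the 80% minimum unless that simulation supports it.

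The cost is one simulation, some wording and a less favourable stated power. The correction itself requires no change in enrolment.
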